#### 3.2. Background

Ciprofloxacin is a synthetic fluoroquinolone antibiotic with activity against Gram positive and Gram negative bacteria. Ciprofloxacin exerts its bactericidal effect by inhibition of Topoisomerase II (DNA gyrase) and Topoisomerase IV, thus interfering with bacterial DNA replication, repair, transcription and recombination. The mechanism of action of fluoroquinolones including Ciprofloxacin differs from other antibiotic classes such as penicillins, cephalosporins, aminoglycosides, macrolides, and tetracyclines therefore, microorganisms resistant to these classes of antibiotics are usually susceptible to fluoroquinolones. The converse applies where microorganisms resistant to Ciprofloxacin are usually susceptible to the other classes of antibiotics [[APO-CIPROFLOX Package Insert, 2012](#)].

#### Indications and Dosing

Ciprofloxacin is used to treat a wide number of infections because of its wide antibacterial spectrum, extensive tissue distribution, prolonged half-life, good oral absorption and lack of cross-resistance with other antibacterials [[Morera, 2001](#)].

Ciprofloxacin is indicated for treatment of infections caused by susceptible strains of the causative microorganisms. Factors which determine the dose include the indication, severity, site of the infection and the renal function of the patient. In children and adolescents the body weight is also taken into account. The duration of treatment depends on the severity of the illness and on the clinical and bacteriological course. Doses may range from a single 500 mg dose once off for Gonococcal urethritis and cervicitis, to 750 mg twice daily taken for a maximum of 3 months for bone and joint infections. In some infections or infection sites higher ciprofloxacin doses and co-administration with other appropriate antibacterial agents is required [[CIPROXIN Package Insert, 2016](#)].

#### Clinical Pharmacology

Ciprofloxacin tablets dissolve rapidly in the gastrointestinal tract following oral administration, and are absorbed in the duodenum and jejunum. Following oral dosing, the bioavailability of ciprofloxacin is 70-80%. Ciprofloxacin bioavailability was unaltered by food. [[Shah, 1999](#)]. Concurrent intake of foods and cations such as iron,

calcium and magnesium result in prolongation of the time to reach peak serum levels [Morera, 2001]. It is therefore recommended that ciprofloxacin should not be taken with dairy products (e.g. milk, yoghurt) or mineral-fortified fruit-juice [CIPROXIN Package Insert, 2016].

Following a 500 mg dose, maximum serum concentrations ( $C_{max}$ ) ranging between 1.5 to 2.9mg/L, are reached within 1-2 hrs following dosing. [Shah, 1999]. Protein binding is 20-30%, and ciprofloxacin is present in the plasma in a non-ionized form, it diffuses freely into the extravascular space [CIPROXIN Package Insert, 2016] . After oral administration, ciprofloxacin is widely distributed throughout the body. Tissue concentrations often exceed serum concentrations in both men and women, particularly in genital tissue including the prostate. Ciprofloxacin is present in active form in the saliva, nasal and bronchial secretions, mucosa of the sinuses, sputum, skin blister fluid, lymph, peritoneal fluid, bile, and prostatic secretions [CIPRO Package Insert, 2011].

The total ciprofloxacin area under the serum concentration versus time curve (AUC) increases in proportion to dose. Four metabolites have been reported, in the urine identified as desethyleneciprofloxacin (M1), sulphociprofloxacin (M2), oxociprofloxacin (M3) and formylciprofloxacin (M4). M1 to M3 display antibacterial activity comparable to or inferior to that of nalidixic acid, while M4, with the smallest quantity, is largely equivalent to norfloxacin in its antimicrobial activity. [APO-CIPROFLOX Package Insert, 2012].

Ciprofloxacin is an inhibitor of cytochrome P450 1A2 (CYP1A2) mediated metabolism. Clinically significant AEs of any drug metabolized by CYP1A2 can occur if co-administered with ciprofloxacin, due to increased plasma concentrations of the co-administered drug [CIPRO Package Insert, 2011]. Co-administration with tizanidine is contra-indicated, since co-administration may increase the serum concentrations of tizanidine leading to tizanidine induced side effects (hypotension, somnolence, drowsiness). Refer to Ciproxin label for products that are contra-indicated.

Ciprofloxacin is predominantly renally excreted with approximately 40 to 50% of an orally administered dose recovered as unchanged drug in the urine with excretion virtually complete within 24 hrs after dosing. Renal clearance is between 180-300 mL/kg/h and the total body clearance is between 480-600 mL/kg/h. Approximately 20 to 35% of an oral dose is recovered from the faeces within 5 days after dosing with 1-2% of the dose is recovered from the bile as metabolites. In humans with normal renal function, the serum elimination half life ( $t_{1/2}$ ) is approximately 4-7 hours. In severely renally impaired subjects the ciprofloxacin half-life is increased up to 12 h [CIPROXIN Package Insert, 2016].

A detailed description of the chemistry, pharmacology, efficacy, and safety of ciprofloxacin is provided in the package insert for Ciproxin .

### **3.3. Benefit/Risk Assessment**

Ciprofloxacin was first approved as an antibacterial agent by the Medicines and Healthcare Product Regulatory Agency (MHRA), in the United Kingdom (UK) in 1987 [[CIPROXIN Package Insert, 2016](#)]. The safety profile of ciprofloxacin is well established based on clinical trial safety data and unsolicited pharmacovigilance reports. More detailed information about the known and expected benefits and risks and reasonably expected AEs of Ciprofloxacin may be found in the Summary of Product Characteristics (SmPC) [[CIPROXIN Package Insert, 2016](#)].

The following section outlines the risk assessment and mitigation strategy for this protocol.

#### **3.3.1. Risk Assessment**

The potential risks of clinical significance for Ciprofloxacin tablets are derived from the prescribing information from marketed formulations during chronic therapeutic use. Most of these reported risks are uncommon, rare or very rare. The likelihood of these risks in a healthy volunteer population receiving a single dose is therefore expected to be lower.

Risks associated when co-administered with other medications are not included as this is an acute dose study in healthy participants.

**Table 2 Summary of Risks and Mitigation Strategies for Investigational Products**

Potential Risk of Clinical Significance	Summary of Data/Rationale for Risk	Mitigation Strategy
Investigational Product (IP) [GR37547]		
Allergic reactions	
Contraindication: Anaphylaxis and anaphylactic shock which may be life threatening may occur if a volunteer has an allergy to the active substance ciprofloxacin, excipients, or other quinolones. Hypersensitivity reactions have been reported following the first dose. Some reactions reported include cardiovascular collapse, loss of consciousness, tingling, pharyngeal or facial oedema, dyspnoea, urticaria, and itching.
 
Other hypersensitivity reactions include fever, rash, severe dermatologic reactions (e.g. Stevens-Johnson syndrome); vasculitis; arthralgia; myalgia; serum sickness; or allergic pneumonitis.
	
Exclude participants with a known history of hypersensitivity to quinolones, ciprofloxacin, or excipients including cellulose microcrystalline, crospovidone, maize starch, magnesium stearate, silica colloidal anhydrous, hypromellose, macrogol and titanium dioxide.
 
Further doses must be discontinued if a participant develops skin rash, jaundice, or any other sign of hypersensitivity following the study medication, and supportive measures immediately instituted.
 
In the event of serious anaphylactic reactions, epinephrine must be given immediately. Oxygen, intravenous steroids, and airway management, including intubation, should be administered as required.

Potential Risk of Clinical Significance	Summary of Data/Rationale for Risk	Mitigation Strategy
Tendinopathy and Tendon rupture	
Warning: Fluoroquinolones, including Ciprofloxacin, are associated with an increased risk of tendinitis and tendon rupture in all ages. Although reports of this adverse reaction (AE) have most frequently involved the Achilles tendon, tendonitis of other sites such rotator cuff (the shoulder), the hand, the biceps, the thumb have also occurred. The risk is higher for older patients (>60 years of age), patients on corticosteroids, patients with rheumatoid arthritis, and those with kidney, heart or lung transplants; however there have been reports of tendonitis in patients with no risk factors.
 
Cases have been reported up to several months after discontinuation of ciprofloxacin therapy.
	
Only healthy participants ≤60 years of age will be included.
 
Participants will be cautioned to avoid strenuous physical activity during participation in this study.

Photosensitivity reactions	Precaution: Ciprofloxacin may cause photosensitivity /phototoxicity reactions of the skin including exaggerated sunburn reactions (e.g. burning, erythema, exudation, vesicles, blistering and oedema).	Study participants will be advised to avoid direct exposure to sunlight and UV radiation such as sunbeds for 24 hours after dosing.
Safety of Ciprofloxacin has not been established in patients under the age of 18 years, pregnant women and nursing women.	
Warning: Ciprofloxacin is excreted in human milk; therefore infants of nursing mothers on ciprofloxacin may be at risk.
 
Damage to juvenile weight-bearing joints and lameness were observed both in rat and dog studies. Permanent lesions of the cartilage were observed on histopathological examination of weight bearing joints of immature dogs.
	Exclude participants ≤18 years of age, pregnant women and nursing women. Contraception guidance is provided in the Participant Information Leaflet.
Musculoskeletal reactions and exacerbation of Myasthenia Gravis	Warning: Muscular skeletal pain, and arthralgia may	Only healthy volunteers will be enrolled.

Potential Risk of Clinical Significance	Summary of Data/Rationale for Risk	Mitigation Strategy
	
occur. Rare instances (<math>\geq 1/10000 < 1000</math>) of myalgia, arthritis and increased muscle tone and cramping have been reported.
 
Fluoroquinolones, including ciprofloxacin, have neuromuscular blocking activity and may exacerbate muscle weakness in persons with myasthenia gravis with resultant requirement for ventilatory support, or resultant death.
	
Prolongation of QT interval	
Warning: Ciprofloxacin may cause tachycardia, ventricular arrhythmia or QT interval prolongation in patients with risk factors for QT interval prolongation such as:
 
 
the elderly and women,
 
patients on concomitant medication such as class IA or III antiarrhythmics, tricyclic antidepressants, macrolides, antipsychotics
 
those with congenital long QT syndrome
 
uncorrected electrolyte imbalance (hypokalemia and hypomagnesemia)
 
Cardiac disease (eg. heart failure, myocardial infarction, bradycardia)
 
	
Participants older than 60 years of age will be excluded, and those with cardiac disease, electrolyte imbalance (Hypokalaemia, hypomagnesaemia), and known risk factors for Torsades des pointes. Only healthy participants will be included. ECG measurements taken during screening and post dose for each period where ciprofloxacin is administered.

Central Nervous System (CNS) Reactions	
Warning: Ciprofloxacin could trigger headache, dizziness, tremors, restlessness, sleep disorders or taste disorders. Ciprofloxacin may affect reaction time and thus the ability to drive or operate machinery may be impaired.
 
Rare cases (<math>\geq 1/10000</math> to <math>< 1/1000</math>) tremor and seizures (including stats epilepticus) have also been
	
Only healthy volunteers will be included, participants with a history of psychiatric conditions (including depression, anxiety, psychosis) will be excluded.
 
Participants will be advised against driving or operating machinery for 24 hours following the dose of study medication.

Potential Risk of Clinical Significance	Summary of Data/Rationale for Risk	Mitigation Strategy
	
reported.
 
Psychiatric reactions may occur including anxiety, paranoia, depression, confusion, psychoses, hallucinations, depression, nervousness, agitation, insomnia, anxiety, paranoia, nightmares and rarely, suicidal thoughts or acts. Depression or psychotic reactions can progress to suicidal ideations/thoughts and self-injurious behaviour, such as attempted suicide or completed suicide.
 
There have also been very rare cases (<1/10000) of migraine, disturbed coordination, gait disturbance, olfactory nerve disorders, intracranial hypertension and increased intracranial pressure (including pseudotumour cerebri).
	

Potential Risk of Clinical Significance	Summary of Data/Rationale for Risk	Mitigation Strategy
Peripheral Neuropathy	Rare cases of sensory or sensorimotor axonal polyneuropathy affecting small and/or large axons resulting in paresthesias, hypoesthesia, dysesthesias and weakness have been reported in patients receiving quinolones, including ciprofloxacin.	Further ciprofloxacin doses will be discontinued if any participant experiences symptoms of neuropathy including pain, burning, tingling, numbness, and/or weakness, or is found to have deficits in light touch, pain, temperature, position sense, vibratory sensation, and/or motor strength in order to prevent the development of an irreversible condition.
Vision disorders	Warning: Impaired vision such as diplopia and colour distortions may also occur.	Study participants will be advised to immediately report any signs of visual disturbances to the investigator.
Hearing disorders	Precaution: There have been rare cases of tinnitus, or transitory deafness (especially at higher frequencies) with ciprofloxacin.	Study participants will be advised to immediately report any signs of hearing disturbances to the investigator.
Metabolic reactions	
Precaution: Hypoglycaemia can occur in Diabetic patients.
 
Ciprofloxacin may increase the effects of caffeine, and result in caffeine accumulation if consumed concomitantly with quinolones.
	
Only healthy volunteers to be enrolled. Exclude volunteers with known or suspected Diabetes based on history, and investigator discretion following review of fasting blood glucose results.
 
All participants to be advised to avoid caffeine containing food and beverages for 24 hours prior until 24 hours following dosing with ciprofloxacin.

Gastrointestinal reactions	Warning: Nausea and diarrhoea are the most commonly reported adverse drug reactions with Ciprofloxacin treatment. Cases of painful oral mucosa, oral candidiasis, dysphagia, intestinal perforation, gastrointestinal bleeding and loss of	Participants will be monitored closely, and appropriate therapy initiated immediately if any symptoms appear. Participants will be asked to contact the site if any symptoms appear within 24 hours after discharge.

Potential Risk of Clinical Significance	Summary of Data/Rationale for Risk	Mitigation Strategy
	
appetite has also been reported. Vomiting, abdominal pain, dyspepsia and flatulence although uncommon (<math>\geq 1/1000</math> to <math>1/100</math>) have been reported. Severe and persistent diarrhoea may occur during or after treatment (including several weeks after treatment). The antibiotic associated colitis could be life threatening with a fatal outcome. Very rare cases of pancreatitis (<math><1/10000</math>) have been reported.
	
Renal and urinary reactions	
Warning: Rare Cases (<math>\geq 1/10000</math> to <math><1/1000</math>) of renal failure, crystalluria, haematuria, tubulointerstitial nephritis have been reported.
	
Healthy participants with normal renal function as determined by review of creatinine clearance, at screening will be enrolled.
 
Participants will be advised to stay well hydrated in the 24 hours following dosing.

Hepatobiliary reactions	
Warning: Cases of hepatic necrosis and life threatening hepatic failure have been reported with ciprofloxacin.
 
Patients with previous liver damage may have an increase in transaminases, alkaline phosphatase or cholestatic jaundice.
	
Participants will be closely monitored for 24 hours following treatment and advised to immediately report any signs and symptoms of hepatic disease such as anorexia, jaundice, dark urine, pruritus or tender abdomen. Laboratory biochemistry results will be reviewed for increases in transaminases, alkaline phosphatase or bilirubin. Any increases to <math>> ULN</math> from baseline levels, following the first dose, will result in discontinuation from further dosing of study treatment based on PI discretion.

Respiratory disorders:	
Precautions: dyspnoea, epistaxis, laryngeal or pulmonary oedema, hiccup, haemoptysis, bronchospasm, pulmonary embolism have occurred in < 1% of patients taking ciprofloxacin.
	
Participants will be closely monitored for any respiratory disorders and, treatment initiated if indicated.

Blood and Lymphatic system reactions	
Eosinophilia, Leukopaenia, anaemia, neutropaenia, leukocytosis and thrombocytopenia may occur
	
All potential participants will be tested for glucose -6-phosphate dehydrogenase at screening and those

Potential Risk of Clinical Significance	Summary of Data/Rationale for Risk	Mitigation Strategy
	
following ciprofloxacin.
 
Haemolytic reactions could occur in patients with glucose-6-phosphate dehydrogenase deficiency.
 
Very rare cases (<1/10000) of agranulocytosis, pancytopenia, and bone marrow depression (life threatening) have been reported.
	
with values below normal will not be entered into the study.
 
All participants will be examined for clinical signs and laboratory signs of haemolysis, so that immediate treatment can commence.
 
Physical signs of haemolysis include weakness, fatigue, pale skin, fainting, shortness of breath, rapid heart rate and dark urine. All participants will be asked to report any of these immediately.
 
Laboratory signs of haemolytic anaemia include hemoglobinuria, a reduction in red blood cell count and haemoglobin and increase in reticulocyte count, lactate dehydrogenase and bilirubin levels.
 
Post dose haematology results will be reviewed for any other blood abnormalities.

Inhibition of Cytochrome P450 (CYP 450)	
Ciprofloxacin is a moderate inhibitor of CYP450 and the CYP1A2 enzyme pathway. Co administration of ciprofloxacin and other medications primarily metabolized via the same metabolic pathways (e.g. theophylline, methylxanthines, tizanidine, clozapine, duloxetine and also caffeine) results in increased plasma concentrations of the coadministered medications and could lead to clinically significant pharmacodynamic side effects of the coadministered medications.
	
Healthy volunteer study, with no concomitant treatments, other than those allowed in Section 7.7 during participation in the study, therefore no drug/drug interactions are expected.

Potential Risk of Clinical Significance	Summary of Data/Rationale for Risk	Mitigation Strategy
Study Procedures		
Blood sampling	An intravenous cannula will be inserted into participants to obtain blood samples for testing. This may cause some pain, discomfort, bruising and redness/irritation at the site of injection.	Participants will be monitored closely by the site staff during the visits. The cannula will be removed if this is causing pain and discomfort. If the cannula is removed, the subsequent blood samples will be collected by venepuncture or the cannula will be replaced.
Other		
Not applicable	Not applicable	

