**Table 1 Schedule of Activities**

Procedure	Screening (Day -21 to Day -1)	Treatment Periods 1 and 2			Follow-up (within approximately 7 days post last dose or at discontinuation)	Notes
		Day -1	Day 1	Day 2		
Informed consent	X					
Inclusion and exclusion criteria	X	X				Refer to Section 6 . Recheck clinical status before randomization. and
Admission to the Unit (domiciled)		X	X	X		Participants to be admitted on Day -1 of each treatment period, and discharged on Day 2.
Outpatient Visits	X					
Discharge				X		
Participants will be discharged from the unit after the collection of the 24 hour post dose PK sample, vital signs (VS), lab assessments and, urinalysis; following review by a doctor to assess participant safety.
 
At the end of treatment period 2, in addition to the other assessments taken at 24 hours post dose (Day 2), all participants will also have an ECG and urine pregnancy test (females), prior to discharge.
 
Participants who have normal safety assessment results at the end of treatment period 2 do not require a follow up.

Procedure	Screening (Day -21 to Day -1)	Treatment Periods 1 and 2			Follow-up (within approximately 7 days post last dose or at discontinuation)	Notes
		Day -1	Day 1	Day 2		
Follow up (Phone Call or Outpatient Visit)					X	If a participant's safety assessments (medical exam, VS, ECG, Lab assessments) are abnormal and clinically significant at Treatment Period 2 discharge, then a follow up phone call or outpatient clinic visit is required within 7 days. Enquiries on the participant's general health, including any AEs/SAEs/concomitant medication should be recorded in the medical notes.
Demography and Medical history (includes substance usage)	X					Substances: Drugs, Alcohol, tobacco and caffeine
Full physical examination including height and weight	X	X				Abbreviated physical exam (excluding height and weight) performed at Day -1
Past and current medical conditions	X	X				
Pregnancy test (WOCBP only)	X	X		X		Serum $\beta$ -hCG: at screening. Urine $\beta$ -hCG: at Day-1 and at the end of Treatment period 2 on Day 2 .
HIV, Hepatitis B and C screening	X					Testing for Hepatitis B (HBsAg) and Hepatitis C (HepC antibody) at screening is not required if this was performed within 3 months prior to first dose of study treatment. Participants, who are positive for Hepatitis C antibody due to prior resolved disease, must have a confirmatory negative Hepatitis C RNA test.

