Procedure	Screening (Day -21 to Day -1)	Treatment Periods 1 and 2			Follow-up (within approximately 7 days post last dose or at discontinuation)	Notes
		Day -1	Day 1	Day 2		
Laboratory assessments (include liver chemistries)	X	X		X		
Screening: Participants are required to fast at least 10 hours prior to the Screening Laboratory assessment. Haematology, Biochemistry, glucose -6-phosphate dehydrogenase, Coagulation profile (PT and aPTT) and Urinalysis are assessed.
 
Day -1: Haematology, Biochemistry and Urinalysis are assessed.
 
Day 2: Haematology, Biochemistry and Urinalysis samples are obtained 24 hours post dose, prior to discharge. Additional safety labs must be collected as deemed necessary at the Investigator's discretion.

Urine Drug/Urine Cotinine/Breath alcohol	X	X				
12-lead ECG a	X		X	X		
12-lead ECG will be completed at:
 
 
• Screening,
 
• Day 1: ECG 2h post dose ( <math>t_{max}</math> ) to be completed before vital signs and 2 hour PK sample.
 
• Day 2: at discharge, at the end of Treatment Period 2 prior to the last PK sample
 
• Follow up: only required if the ECG at discharge was abnormal and clinically significant ECGs to be taken <math>\pm 30</math>min of time points specified
 

Procedure	Screening (Day -21 to Day -1)	Treatment Periods 1 and 2			Follow-up (within approximately 7 days post last dose or at discontinuation)	Notes
		Day -1	Day 1	Day 2		
Vital signs a	X		X	X		
Vitals will be taken at:
 
 
• Screening,
 
• Day 1: pre-dose and post dose at, 2.00, 4.00, and 6.00 hours
 
• Day 2: 24.00 hours post-dose.
 
 
Post dose vitals to be taken <math>\pm</math>30min of each time point.

Randomization			X			Day 1 of treatment period 1 only.
Study treatment			X			Screening and Day -1 results must be reviewed by physician prior to randomisation and dosing. Participants to be fasted 10.00 hours prior and 4.00 hours post dose. Dosing between Treatment periods will be separated by a washout of 7 -14 days. Participants will remain in a sitting or semi-supine position for at least 4 hours after dosing on Day 1 of each treatment period.

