AE Review		$\leftarrow-----\rightarrow$				Collected from the start of dosing (Day 1, Treatment period 1) to the participant's final discharge from study at the end of Treatment Period 2, follow up call or last outpatient visit, whichever is the latest.
SAE review		$\leftarrow-----\rightarrow$				Any SAEs assessed as related to study participation (e.g. investigational product, protocol-mandated procedures, invasive tests) or related to a GSK concomitant medication will be recorded from the time a participant consents to participate in the study up to and including any follow up contact.

Procedure	Screening (Day -21 to Day -1)	Treatment Periods 1 and 2			Follow-up (within approximately 7 days post last dose or at discontinuation)	Notes
		Day -1	Day 1	Day 2		
Concomitant medication review		←=====→				
Pharmacokinetics a			X	X		
Day 1: Pre-dose, 0.50, 0.75, 1.00, 1.25, 1.50, 1.75, 2.00, 2.50, 3.00, 3.50, 4.50, 6.00, 8.00, 12.00, 18.00 hours
 
Day 2: 24.00 hours post dose
 
Pre-dose sample will be taken within 15 minutes before dose. Post dose samples for:
 
 
• 0.500 -2.00 hours will be taken <math>\pm 2</math> min; ;
 
• 2.50 – 8.00 hours will be taken <math>\pm 5</math> min; and
 
• 12.00 – 24.00 hours will be taken <math>\pm 10</math> min.
 

a. The order of assessments to be followed where an ECG, Vital Signs and Blood sample for either PK or Lab assessments are required at the same time point, should always be first ECG, second vital signs and lastly blood sampling, whilst ensuring that the timing for PK blood samples remains within the sampling window.

- Any changes in the timing or addition of time points for any planned study assessments must be documented and approved by the relevant study team member and then archived in the sponsor and site study files, but will not constitute a protocol amendment. The Institutional review board (IRB)/ Independent ethics committee (IEC) and regulatory authority will be informed of any safety issues that require alteration of the safety monitoring scheme or amendment of the informed consent form (ICF).
- AE= Adverse Event; aPTT= Activated Partial Thromboplastin Time; ECG= Electrocardiogram; GSK= GlaxoSmithKline; HIV= Human Immunodeficiency Virus; hr= Hour; IP= Investigational Product; PK= Pharmacokinetic; PT= Prothrombin Time; SAE= Serious adverse event(s)

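### The gastrointestinal row of Table 2 warns of severe diarrhoea weeks after treatment, but its contact request ends 24 hours after discharge; with normal Period 2 results, only passive notification of related SAEs remains after that.

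*Combined protocol and SAP*

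**What the plan says.** The gastrointestinal row of Table 2 describes the hazard this way: "Severe and persistent diarrhoea may occur during or after treatment (including several weeks after treatment". It adds: "The antibiotic associated colitis could be life threatening with a fatal outcome". On the mitigation side, the row promises close monitoring and prompt therapy. It then makes one request of participants: "Participants will be asked to contact the site if any symptoms appear within 24 hours after discharge".

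The Schedule of Activities (Table 1) sets the time frame around that request:

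- Discharge in each period: "Participants will be discharged from the unit after the collection of the 24 hour post dose PK sample", together with the other Day 2 safety assessments and a doctor's review.
- Between the two doses: "Dosing between Treatment periods will be separated by a washout of 7 -14 days".
- After Period 2: "Participants who have normal safety assessment results at the end of treatment period 2 do not require a follow up". A phone call or clinic visit within 7 days is required only when a safety assessment at Period 2 discharge is abnormal and clinically significant.
- AE review starts with the first dose and runs to "final discharge from study at the end of Treatment Period 2, follow up call or last outpatient visit, whichever is the latest".

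Section 9.2.1 does not oblige investigators to look for events in former participants. It does require prompt notification of any SAE that they learn of after discharge and consider reasonably related, with no time limit.

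**The concern.** The warning and the request sit in the same table row but work on different time scales. The warning is measured in weeks; the request is measured in hours. A participant who follows the request as written has no reason to call about diarrhoea that begins on, say, day 10 after the second dose, and a reader could take the stated limit to mean that later symptoms need not be reported.

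What is at stake is participant safety and, secondarily, the capture of late adverse events. Safety results at 24 hours after dosing cannot show diarrhoea that has not yet begun, so making follow-up depend on those results does not address late onset. The outcome named in the row is one where an early call to the site would matter.

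**Working it through.** The plan gives no calculated figure on this point. The check is simple addition of stated times, followed by a comparison of provisions.

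**Times**

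1. End of the contact request. Discharge at about 24 h after dosing (Table 1, Discharge) plus 24 h (Table 2, gastrointestinal row): 24 + 24 = 48 h, or about 2 days after the dose.
2. AE review after the first dose, for a participant who continues. Washout of 7 to 14 days (Table 1, Study treatment) plus about 1 day to Period 2 discharge: 7 + 1 = 8 days to 14 + 1 = 15 days.
3. AE review after the second dose. With normal Period 2 results it ends at final discharge, about 1 day after the dose. With abnormal and clinically significant results, one call or visit follows within 7 days.
4. The warned period. The row says several weeks and gives no number. Even if that is read as only two weeks (an assumption, and a short reading), 14 days is later than both the 2 days in step 1 and the 7 days in step 3.

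The first dose is therefore partly covered, because the participant returns for Period 2 while AE review is still open. The gap concerns the time after the second dose, in a participant with normal results, from about 48 h onwards.

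**Does another provision fill the gap?**

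- Section 9.2.1: notification of a related SAE has no time limit, but applies only if the investigator learns of the event. Nothing prompts the participant to supply that information.
- Section 9.2.3: follow-up to resolution begins after an initial report. It does not produce the report.
- Section 9.4.4: repeat testing is triggered by a clinically significant laboratory abnormality during participation or within 7 days of the last dose. Diarrhoea alone does not trigger it.

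I found no other place in the protocol or its analysis plan that asks participants to report late diarrhoea.

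**How do the other rows of Table 2 word their requests?**

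- Vision and hearing: immediate reporting of any disturbance, no stated end.
- Hepatobiliary: immediate reporting of signs such as jaundice or a tender abdomen. The 24 hours in that row refers to monitoring, not to the request.
- Blood and lymphatic: immediate reporting of signs of haemolysis, no stated end.
- Sunlight, driving, caffeine and hydration: 24-hour limits, but on precautions and not on reporting.

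Among the requests to report symptoms, only the gastrointestinal one has an expiry, and its own row describes onset well beyond it.

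**The case against.** Four arguments can be made for leaving the text alone.

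*The risk is small here.* Section 3.3.1 says that the Table 2 risks come from labelling for chronic therapeutic use, and states: "The likelihood of these risks in a healthy volunteer population receiving a single dose is therefore expected to be lower". Setting follow-up to the expected risk of two single tablets, and not to the longest label warning, is a defensible design choice. This stands, and it is why the point carries little weight and why no extra visit is proposed. It does not explain why the row limits a telephone request to 24 hours when neighbouring rows set no limit.

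*Instructions to participants belong in the leaflet.* The protocol already uses the leaflet for contraception guidance, and the leaflet and consent text were not available for review. This also stands. The point is about the protocol wording only; if the leaflet already tells participants to call about late diarrhoea, the change is one of alignment.

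*Serious events are already caught.* Colitis grave enough to be life-threatening would be an SAE, and Section 9.2.1 keeps notification of related SAEs open indefinitely. That is correct as a reporting duty for the investigator. It is not a prompt to the participant, so the route depends on an unprompted call.

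*The remedy is selective.* The tendon row mentions cases several months later and contains no reporting request at all. That is fair, and the sponsor may wish to look at that row too. The gastrointestinal row differs in that it states a limit which its own warning exceeds.

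**Conclusion.** The point holds in a limited form. For a participant with normal Period 2 results, diarrhoea that starts more than 24 hours after final discharge (about 48 hours after the second dose) has no protocol-stated participant instruction and no planned follow-up. Only passive notification of a related SAE remains. This could apply to any of the approximately 26 participants. The documents give no rate of late diarrhoea after a single dose, so no number of events is claimed.

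A reader might infer more than this, and three stronger readings should be resisted:

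- *That all onset after final discharge is uncovered.* The contact request itself covers the first 24 hours after discharge, and Section 9.2.1 covers related SAEs that become known later.
- *That the uncovered share of the risk can be given as a percentage.* Several weeks is undefined, and a share of elapsed time equals a share of risk only if onset is spread evenly over the window. Nothing in the documents supports that.
- *That Table 2 in general cuts reporting off at 24 hours.* The other 24-hour limits concern precautions or monitoring.

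The conclusion assumes only that several weeks means longer than the planned contact after the second dose. It is a low-cost safety improvement to consider. The bioequivalence endpoints, their analysis and the sample size are unaffected.

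**What to change.** In the gastrointestinal row of Table 2, keep the existing 24-hour sentence for any symptoms and add one after it, along these lines: *Participants will also be asked to contact the site immediately if severe or persistent diarrhoea, or blood in the stool, appears at any time during the study or in the weeks after the last dose (for example up to 8 weeks; sponsor to set).* The 8 weeks is only an illustration, since the documents give no figure. Check that the participant leaflet says the same, and amend it if it does not.

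A sentence in Section 9.2.1 on how a late, non-serious report is recorded is optional. That section already deals with serious related events after discharge, and the point does not depend on the addition.

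The cost is one sentence and a leaflet check, with no added visit or procedure. The downside is a few more calls to the site. Obligations that outlast discharge are not new to this protocol: Section 6.1 already asks for contraception for at least 30 days after the last dose in women of childbearing potential and at least 5 days in men.
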